- 472 The main objectives of this aim are to:
- Establish the normal hepatic blood flow and portal compliance in the human liver
- Determine the relationship between hepatic flow and pressure, and graft size and function
 and clinical outcomes in living donor liver transplantation
- Establish the benefit, if any, of portal flow modulation interventions on hepatic compliance,
 and functional and clinical outcomes.

478 **3.4.1.1 Hypotheses:**

- It is generally thought that the limits of portal compliance are exceeded when graft size is less than 40% of normal (<.8% of liver/recipient body weight ratio (BWR). We hypothesize that grafts smaller than this limit will demonstrate altered hemodynamics, limited compliance, and impaired function.
- We hypothesize that restoration of pressure and flow in the "normal" range will permit grafts
 below 0.8% BWR to function normally with good results.

485 486

487 **3.5.1 Objectives**

- 488 To determine whether recurrent hepatitis C in LDLT recipients is associated with less severe
- 489 histological fibrosis (particularly, slower rate of progression to cirrhosis) compared to DDLT
- 490 recipients.

491 **3.5.1.1 Hypothesis:**

Living donor liver transplant (LDLT) recipients will demonstrate slower rate of progression to
cirrhosis than deceased donor liver transplant (DDLT) recipients as determined by histology. Given
that little difference has been seen in the initial 3 years post-transplant, we anticipate that any
difference will be expressed more than three years post-transplant.

496 497 3.6 Primary Aim 6: To understand the history of pain management and to measure quality 497 of care in pain control in living donors following partial hepatectomy.

498 **3.6.1** Objectives

499	• To understand each institution's previous experience with pain management in living
500	donors utilizing a retrospective survey (see Appendix E) of appropriate medical staff
501	to:
502	• Determine all methods and personnel at each center used to manage
503	postoperative pain in live liver donors since the start of their program
504	• Identify how pain was assessed during the postoperative period (current and
505	previous assessment methods)
506	• Identify methods care providers used to assess the outcome (quality) of pain
507	management.
508	• To measure the quality of postoperative pain management in live liver donor and
509	identify areas for improvement. After implementing a single method (patient survey

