1264 4.6.1.7 Statistical Analysis

- 1265 Retrospective Component:
- 1266 The methods and personnel that each center uses to manage postoperative pain in live liver donors
- 1267 and methods they have stopped using, will be presented using descriptive statistics. If possible,
- 1268 graphical methods will be used to display the changes over time.

1269 The medical specialty of care providers responsible for pain management and assessment will also

- be described for the 9 A2ALL centers. This summary will include both the type of specialists
 involved, and whether pain management involved an Acute Pain Team or not. Both the proportion
- 1271 of centers with Acute Pain Teams and the composition of these teams will be described. The
- 1273 continuity of pain management through phases of patient locations (e.g., ICU, surgical ward) will
- 1274 also be reported. Finally, the opinion of the medical care providers on the adequacy of pain control
- 1275 at their center will be described, and will also be compared to patient reports at that center (using
- 1276 data from prospective component of the study).
- 1277 Prospective Component:
- 1278 Satisfaction will be assessed using (a) the single question (P9), measuring overall satisfaction, and
- (b) the individual items of the pain questionnaire (P1-P8 and P10-12). These outcomes will be

1280 presented using descriptive statistics, including frequencies, means and standard deviations.

1281 Histograms and/or boxplots will be used to identify the forms of the distributions and to identify

- 1282 outliers. Aspects of care with low scores or a large standard deviation will be identified as practices
- 1283 that require overall improvement. Boxplots and analysis of variance will also be used to display and
- 1284 compare quality indicators from the APS-POQ-R measures by center.
- 1285 To identify aspects of care that account for differences in patient satisfaction, we will evaluate 1286 predictors of overall satisfaction (P9) using linear regression. Predictors of overall satisfaction to be
- 1287 tested will include the pain relief variables (P1-P7), participation in decisions about pain treatment
- 1288 (P8), helpfulness of information received (P10), non-medicine methods of treatment (P11, P12),
- 1289 demographic variables, and donor relationship.
- 1290 The complications outcomes (P6) will be analyzed using descriptive statistics as described above.

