22. Pain is assessed frequently enough on the ward.
O Strongly agree
O Somewhat agree
Somewhat disagree
Strongly disagree
23. The severity of pain experienced by live liver donors is greater than other liver
resection patients.
O Strongly agree
Somewhat agree
Somewhat disagree
Strongly disagree
24. The amount of emotional distress experienced by live liver donors due to pain is
greater than other liver resection patients.
Strongly agree
O Somewhat agree

25. Health care providers often under treat pain in live liver donors because they are
worried about complications of pain medications.
Strongly agree
Somewhat agree
Somewhat disagree
O Strongly disagree
26. Your live liver donors are currently satisfied with their pain management.
O Strongly agree
O Somewhat agree
O Somewhat disagree
O Strongly disagree

C. Approach to Pain Assessment
The following questions ask about how your institiuion evaluates patients' pain.
27. Indicate all health care providers that routinely perform pain assessment in the ICU.
Acute Pain Team
Surgery
Attending anesthesiologist
ICU physician
Don't know
Other (please specify)
28. Indicate all health care providers that routinely perform pain assessment in the PACU.
Nursing
Acute Pain Team
Surgery
Attending anesthesiologist
ICU physician
Don't know
Other (please specify)
29. Please indicate all health care providers that routinely assess pain on the surgical ward.
Acute Pain Team
Attending anesthesiologist
Don't know
Other (please specify)

30. What pain related information is routinely recorded? (only data that would be
retrievable by chart review)
Visual/numerical pain score at rest
Visual/numerical pain score with movement
Sedation scores
Don't know
31. Does your instituion routinely use a standard patient satisfaction survey to assess the
efficacy of pain management?
O Yes
~
32. If your institution does not use a standard survey to assess satisfaction of live donors
with their pain management, now do you assess this information?
Y .

Preoperative Preparation, Patient Input and Ongoing Assessment
These questions are about types of interaction that health care providers have with live liver donors prior to surgery. Area of interest include personal interactions and the development and use of protocols for pain management.
33. Does an anesthesiologist see all live liver donors prior to the day of surgery?
⊖ Yes
O №
34. Does the Acute Pain Team offer to see all live liver donors prior to the day of surgery?
O Yes
O Don't Know

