46. Please check all pain management techniques you currently use in the first 48 hours after surgery. Please provide your opinion regarding each technique listed. If other techniques are used, please list and provide your opinion in the text box that follows the question.

	Epidural	Intrathecal	IVPCA	Local Infiltration			
Safe							
Works well							
Cost Effective							
Uses fewer resources							
No opinion							
Other (please specify)							
47. Please check all oral pain medications you currently use in the first 48 hours after donation and provide your opinion regarding the medication. If other agents are utilized,							
please specify what the agents are and provide your opinion of them.							
	Oral Opioid	Gabapentin/Pregabalin	NSAID	Acetaminophen			
Safe							
Works well							
Cost Effective							
Uses fewer resources							

Other (please specify)

No opinion

48. Has your institution changed pain management techniques since the start of your program?

۸

 $\overline{\Box}$

Ves

O Don't Know

49. If yes, approxim	ately when was	the last time that yo	our program chai	iged techniques?
O Within the last year				
From 1 to 2 years ago				
More than 2 years ago				
50. If you answered	Yes to question	48, how many time	s has your progr	am changed pain
management techn	iques for live live	er donors since the	start of your pro	gram?
O 1				
O 2				
O 3				
O 4				
51. Please check al	l pain control teo	hniques that your c	enter has tried, l	but does not
currently use in the	first 48 hours af	ter donation.		
Epidural				
Intrathecal				
Local Infiltration				
Other (places specify)				
Other (please specify)				
52. Please identify f	the reasons you	do not use any of the	e techniques list	ted below, even if
you have not tried t	hem. If there are	other techniques y	ou feel should be	e included, please
list them and add yo	our reasons for n	lot using them.	IVPCA	Local Infiltration
Patient Complications				
Does not work well				
Not cost effective				
Uses more resources				
Personal choice				
Don't know				
No opinion				
Other (please specify)				
		×		

53. Please check al	l pain medicatio	ons your center has tr	ied, but does no	t currently use in
the first 48 hours af	ter donation.			
Gabapentini/Pregabaini				
O NSAID				
Acetaminophen				
Other (please specify)				
54. Please identify	the reasons you	do not use the listed	medications to	control donor

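### Appendix E has no item on former personnel or former pain-assessment methods, so two parts of the Aim 6 history objective in section 3.6.1 will have no data

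*Protocol*

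**What the plan says.** Section 3.6.1 ties the historical half of Aim 6 to one instrument. Past experience is to be learned for living "donors utilizing a retrospective survey (see Appendix E) of appropriate medical staff". The first task is worded "Determine all methods and personnel at each center used to manage", and its scope is "postoperative pain in live liver donors since the start of their program". The second task is worded "Identify how pain was assessed during the postoperative period (current and"; the parenthesis goes on to name previous assessment methods as well.

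Section 4.6.1.5 lists responses to Appendix E as the only data element of the retrospective component. Section 4.6.1.7 plans descriptive statistics on the methods and personnel each center uses and on the methods it has given up. It adds that, if possible, "graphical methods will be used to display the changes over time".

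In Appendix E, pain assessment is covered by part C (Q27 to Q32), for example Q30, "What pain related information is routinely recorded". The backward-looking block starts at "48. Has your institution changed pain management techniques since the start of your program" and runs to Q54. Q49 asks when the last change took place, and its oldest printed band is "More than 2 years ago".

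**The concern.** The objective and the instrument do not match. An objective that reaches back to the start of each program needs items that ask about the past, and for two of its elements (who managed or assessed pain, and how pain was assessed) Appendix E seems to have none. No later analysis plan can repair this, because analysis cannot recover what the survey never asked.

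If the survey is fielded as printed, the report on Aim 6 would either say nothing about past personnel and past assessment, or present current practice as though it were history. A second, smaller worry is that the planned picture of change over time would rest on a single dated event per center.

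**Working it through.** No sample size, power or error rate is involved. The check compares the objectives with all 55 numbered items.

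| Element promised in section 3.6.1 | Items on current practice | Items on the past |
|---|---|---|
| Personnel | Q5 to Q13, Q17 to Q18, Q27 to Q29, Q33 to Q34, Q37, Q42 to Q45 | None |
| Assessment methods | Q27 to Q32 | None |
| Techniques and medications | Q40, Q46, Q47 | Q48 (any change), Q49 (timing of the last change), Q50 (number of changes), Q51 and Q53 (tried, not now used), Q52 and Q54 (reasons for non-use) |

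**Items that might fill the two empty cells.** Four come close, and none does so:
- Q3 asks for the respondent's own years of experience.
- Q4 asks for the respondent's own donor count over the last 12 months.
- Q36 is worded in the past tense, but asks who helped to write the protocol now in force.
- Q55 is an open comment box that does not ask about either subject.

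**Could a question have been lost in the text?** All numbers from 1 to 55 are present, so no question stem is missing. Some answer options are visibly lost elsewhere in the appendix, but a lost option would not turn a question about present routine into one about the past.

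**What can be dated.** Q49 is the only dating item for changes. The bands that survive in the text are within the last year, 1 to 2 years ago, and the open oldest band. For a center with k changes, Q49 places 1 of k:
- k = 1: 1 of 1, within a one-year band if the change was recent, otherwise with no lower limit on its date.
- k = 2: 1 of 2, so 1 is undated.
- k = 4 (the highest count printed in Q50): 1 of 4, so 4 − 1 = 3 are undated.

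Q51 and Q53 list abandoned techniques and medications without years. Q46 and Q47 list current ones without the year they were introduced.

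**Result.** Past personnel: 0 items. Past assessment methods: 0 items. Past techniques and medications: covered, with a date only for the latest change.

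**The case against.** The other side has good points, and most of them limit the size of the problem.

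- A reader might infer that the history of pain management cannot be described at all. The protocol does not support that. Q48 to Q54 collect whether and how often techniques changed, what was abandoned, and reasons for non-use. The description of stopped methods in section 4.6.1.7 is feasible as written.
- A reader might take the display over time as a firm commitment that must fail. Section 4.6.1.7 makes it conditional on being possible, and a center with a single change in the last two years can be placed within a one-year band.
- The analysis in section 4.6.1.7 speaks of personnel in the present tense and, for the past, only of methods. The introduction to Appendix E likewise announces past methods of pain control, and neither past personnel nor past assessment. Analysis and instrument largely agree, and the wording of section 3.6.1 is the outlier. This stands, and it is why narrowing that section is an acceptable remedy.
- It is tempting to say how much history falls into the oldest band of Q49. For programs assumed to be 10 to 15 years old, the share of elapsed time is (10 − 2)/10 = 80% to (15 − 2)/15 = 87%. The protocol gives no center start dates, and a share of time is not a share of changes or of centers. The figure should not be used as a measure of loss.
- Because answer options are damaged in the text, the exact bands of Q49 and the upper count in Q50 cannot be taken as certain.

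None of this supplies data on former personnel or former assessment methods. Those two promises in section 3.6.1 carry no qualifier.

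**Conclusion.** The point holds in a limited form. Two parts of the Aim 6 objective, personnel since the start of each program and previous assessment methods, have no corresponding item in the only instrument named, and so will have no data at any of the nine centers. The history of techniques and medications is collected, but with only the latest change dated. The conditional display of change over time therefore cannot be built for centers with several changes or with a last change in the oldest band. How many centers that affects cannot be known from the protocol.

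The conclusion assumes that the survey is fielded as printed and that no other source is used, which is what section 4.6.1.5 states. The consequence is confined to description: section 4.6.1.6 sets the unit of analysis as the center, with nine centers and no inference beyond them. No endpoint, power or safety result changes. The mismatch is still worth correcting, because it concerns the stated question of a primary aim and is cheap to remove.

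**What to change.** If the survey is still open, add short items to the web form on:
1. Previous ways of assessing pain, including who assessed it and what was recorded, with the approximate year each ended.
2. Personnel previously responsible for managing pain, with approximate years.
3. Approximate first and last year of use for each current and abandoned technique and medication (those in Q46, Q47, Q51 and Q53).

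Each item needs a don't-know option, since Q3 allows for respondents with under two years' experience. Years attached to each technique would also show which change happened when, which Q49 does not.

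If the survey has closed, send these items as a short supplement. Otherwise, restate section 3.6.1 as current practice plus discontinued techniques and medications, and drop the over-time display from section 4.6.1.7.

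The cost is a modestly longer survey for at most 9 × 3 = 27 respondents (up to three at each center, section 4.6.1.3). Recalled years will be approximate and should be reported as such. Restating the objective costs only a protocol edit, but gives up the history of personnel and assessment.

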8.6 APPENDIX F: Prospective Living Donor Pain Survey

Name of Person Administering Survey			A2	ALL		Subjec	t ID D		
	A	2ALL	. Don	or Pa	ain S	Survey	y [PRINT FORM	
Date of First Attempt Sedation Score 0 = Fully Awake		of self/surrou	Time) AM) PM	Type of Pain M	Manageme Iral hecal	nt (check all that	apply)
2 = Moderate seda	ation, slightly	aware of self/s	surrounds. Soi	mnolent but	easily	Local	Infiltration	1	
\bigcirc 3 = Deeply sedate	d, unaware of nesia, patient i	self/surroundi s unconscious	ings.						
Date of Second Att	empt		Time		O AM	Sedation Sco	re		
P1. On this sca	e, please i	ndicate th	e least pa	iin you ha	ad in the	FIRST 24 h	nours .	11	
0 1 O O	2	3	4	5	6	7 8		9 10 O O	
No Pain	μ							Worst	Possible Pain
P1A. On this sca	le, please	indicate th	ne least p	ain you h	ad in the	e LAST 24 l	nours.		
0 1 O O	2	3	4	5	6	7 8		9 10 O O	
No Pain	J]]]]		Pos	Worst sible Pain
P2. On this sca	P2. On this scale, please indicate the worst pain you had in the LAST 24 hours .								
0 1 • •	2	3	4	5	6 〇	7 8 O (9 10 O	
No Pain								Pos	Worst sible Pain
P3. What perce	ntage of t	ime in the	LAST 24	hours we	ere you ii	n severe p	ain?		
00/	2004	2001	1001		600/				

0%	10%	20%	30%	40%	50%	60%	70%	80%	90%	100%
0	0	0	0	0	0	\bigcirc	0	\bigcirc	0	0
Never in		1-		2	1				A	lways in
severe pain									S	evere pain

							Subj	ect ID D		
P4. Choose the one number below that best describes how much pain interfered or prevented you from:										
a. Doi	ng activiti	es in bea s	uch as turr	ling, sitting	g up, repos	sitioning:	1		1	
0	1	2	3	4	5	6	7	8	9	10
O Does not					\bigcirc			\bigcirc		Completely
interfere										interferes
b. Doing activities out of bed such as walking, sitting in a chair, standing at the sink:										
0	1	2	3	4	5	6	7	8	9	10
0	0	0	0	0	0	0	0	\bigcirc	0	0
Does not interfere										Completely interferes
с. Fal	ling asleep):	ſ	1	1	1	í	1	[
0	1	2	3	4	5	6	7	8	9	10
O Doos not	0	0	\bigcirc	\bigcirc	0	0	\bigcirc	0	0	Completely
interfere										interferes
d Sto	wina aslee	n.								
u. 50		P•	2	4	F	G	7	0	0	10
0		2	5	4	5	0		8	9	
Does not										Completely
interfere										interferes
P5. Pain o On this so	can affect o	our mood a	nd emotio	ns. her that he	st shows h	now much	the nain ha	as caused y	vou to feel·	
	ale, picase	choose the			250 5110 005 1	low mach	the pulling	is caused y		
a. Anxiou	S				_		1_			
0	1	2	3	4	5	6	7	8	9	10
O Not at all					\bigcirc			\bigcirc		Extremely
										Extremely
b. Depres	ssed									
0	1	2	3	4	5	6	7	8	9	10
0	\bigcirc	0	\bigcirc	\bigcirc	\bigcirc	0	\bigcirc	\bigcirc	0	\bigcirc
Not at all										Extremely
c. Frightened										
0	1	2	3	4	5	6	7	8	9	10
0	\bigcirc	0	0	0	\bigcirc	0	\bigcirc	\bigcirc	0	0
Not at all										Extremely

							:	Subject ID	D	
P5. (C	Cont'd)									
On thi	is scale, p	lease cho	ose the c	one num	ber that l	best show	/s how m	uch pain	caused y	ou to feel:
d. Help	oless			11			1			
0	1	2	3	4	5	6	7	8	9	10
		\bigcirc	\bigcirc	\bigcirc	0	0	0	0	0	Extromoly
NOLALA	II									Extremely
P6. Ha	ve you had	any of the	following	side effec	ts?	h a at ah aw		ity of oo ch		
Please	cnoose u	If no; if yes	s, choose t	ine one nu	imper that	best snow	s the sever	ity of each	:	
a. Naus	sea	1	1	1			1	1	1	1
0	1	2	3	4	5	6	7	8	9	10
Nono	0	\bigcirc	\bigcirc	\bigcirc	0	0	0	0	0	C Sovero
None										Jevele
b. Drov	vsiness									
0	1	2	3	4	5	6	7	8	9	10
\bigcirc	\bigcirc	\bigcirc	\bigcirc	\bigcirc	\bigcirc	\bigcirc	\bigcirc	\bigcirc	\bigcirc	\bigcirc
None										Severe
c. Itchiı	ng									
0	1	2	3	4	5	6	7	8	9	10
\bigcirc	0	0	0	0	0	0	0	0	0	\bigcirc
None		 		I		J.			J	Severe
d Dizz	viness									
0	1	2	3	Δ	5	6	7	0	0	10
			5		5	0	, 	0	3	
None										Severe
	the last 24	hours hou	complete	hacvour	nain raliaf	hoon?				
Please	choose the	e one perce	entage tha	t best sho	ws how mi	uch relief y	ou have re	ceived fror	n all of you	ır pain
treatm	ents comb	ined (medi	cine and n	on-medic	ine treatm	ents).				I
0%	10%	20%	30%	40%	50%	60%	70%	80%	90%	100%
0	\bigcirc	\bigcirc	\bigcirc	\bigcirc	\bigcirc	\bigcirc	0	\bigcirc	0	\bigcirc
No Relie	f									Complete Relief

Sul	oject	ID
